8.1.2. Laboratory assays

Table 8 Laboratory assays

Assay Type	System	Component	Method	Laboratory
Screening	Serum	Anti-HSV antibodies	Western Blot	University of Washington Molecular Virology laboratory
Humoral immunity (antibody determination)	Serum	CCI [REDACTED] antibodies	ELISA	GSK* or in a laboratory designated by GSK
Cell-mediated immunity	PBMC	CCI [REDACTED] (CD4+/CD8+) T-cells	CFC	

ELISA: enzyme-linked immunosorbent assay; CCI [REDACTED] HSV: herpes simplex virus;

PBMC: peripheral blood mononuclear cell; CD4+/CD8+: cluster of differentiation 4/8; CFC: cell flow cytometry

* GSK laboratory refers to the Clinical Laboratory Sciences (CLS) in Rixensart, Belgium; Wavre, Belgium.

Please refer to Section 10.2 for a brief description of the assays performed in the study.

The addresses of clinical laboratories used for sample analysis are provided in a separate document accompanying this study protocol.

CCI

Note that tertiary objectives and endpoints/estimands are optional and might be assessed only if needed; therefore, not all related testings might be performed and reported.

CCI

Additional exploratory testing on the disease under study may be performed within the framework of the study if deemed necessary for accurate interpretation of the data or should such assay(s) become available at GSK's laboratory or a laboratory designated by GSK. These assay(s) may not be represented in the objectives/endpoints/estimands of the Protocol and may be described in ancillary study Protocol(s), as needed.

GSK clinical laboratories have established a Quality System supported by procedures. The activities of GSK clinical laboratories are audited regularly for quality assessment by an internal (sponsor-dependent) but laboratory-independent Quality Department.

8.1.3. Immunological read-outs

Table 9 Immunological read-outs

Blood Sampling Timepoint	Sub-cohort Name	Number of Participants	Component
Type of Contact and Timepoint			
Screening	All screened participants	> 50	Anti-HSV antibodies
Humoral Immunity			
Visit 1 (Day 1) Visit 3 (Day 29) Visit 5 (Day 57)	All participants	~ 50	CCI [REDACTED] antibodies
Cell-mediated Immunity			
Visit 1 (Day 1) Visit 3 (Day 29) Visit 5 (Day 57)	All participants	~ 50	CCI [REDACTED] (CD4+/CD8+) T-cells

CCI [REDACTED]; HSV: herpes simplex virus; CD4+/CD8+: cluster of differentiation 4/8

8.1.4. Immunological correlates of protection

No generally accepted immunological correlate of protection has been demonstrated so far for the HSVTI.

8.2. Safety assessments

The investigator(s) and their designees are responsible for detecting, documenting, and reporting events that meet the definition of an AE or SAE. The investigator and designees are responsible for following up AEs that are serious, considered related to the study intervention or the study, or that caused the participant's withdrawal from the study intervention and/or study.

8.2.1. Pre-intervention administration procedures

8.2.1.1. Collection of demographic data

Record demographic data such as year of birth, sex at birth, HSV-1 status, race, and ethnicity in the participant's eCRF during the Screening visit.

Collection of sex, race and ethnicity data is necessary to assess and monitor the diversity of the trial participants, and to determine if the trial participants are truly representative of the impacted population.

8.2.1.2. Measure and record height and weight

Height and weight will be collected during the Screening visit in order to calculate the participant's body mass index (as part of the eligibility criteria). Data will be recorded in the eCRF.

8.2.1.3. Medical and vaccination history

Obtain the participant's medical and vaccination history by interviewing the participant and/or review of the participant's medical records. Record any pre-existing conditions, signs and/or symptoms present prior to the Screening visit in the eCRF.

*The following vaccination history must be checked and recorded, if applicable:

- Any previous administration of an investigational HSV vaccine at any time.
- Any vaccines to be administered between the Screening visit and Visit 1 (Day 1).

8.2.1.4. Perform physical examination

- A physical examination will be performed for each participant at the Screening visit and before each study intervention administration (Visit 1 [Day 1] and Visit 3 [Day 29]). The following information will be recorded in the eCRF: oral body temperature, resting vital signs (before blood collection for laboratory test),

including systolic/diastolic blood pressure, and heart rate after at least 10 minutes of rest.

- A targeted physical examination at each subsequent visit will be performed only if the participant indicates during questioning that he/she might have some underlying pathology(ies) or if deemed necessary by the investigator or delegate. Collected data do not need to be recorded in the eCRF, unless required (see Section 8.3).
- If the investigator determines that the participant's health on the day of study intervention administration (Visit 1 [Day 1] and Visit 3 [Day 29]) temporarily precludes dosing, the visit will be rescheduled within the allowed interval (see Table 2). Refer to Section 5.5 for the list of criteria for temporary delay of study intervention administration.
- Treatment of any abnormality observed during this examination must be performed according to local medical practice outside this study or by referral to an appropriate healthcare provider.

8.2.1.5. Perform pregnancy test

Women of childbearing potential must perform a urine pregnancy test before the administration of any dose of study intervention. Pregnancy testing must be done even if the participant is menstruating at the time of the study visit. The study intervention may only be administered if the pregnancy test is negative.

- Only women with negative pregnancy test result at the Screening visit will be included in the study.
- The study intervention may only be administered if the pregnancy test result is negative at Visit 1 (Day 1) and Visit 3 (Day 29).

For women of non-childbearing potential, the specific reason for not performing a pregnancy test (pre-menarche, bilateral tubal ligation or occlusion, hysterectomy, bilateral ovariectomy, post-menopause or other) needs to be documented in the participant's source document.

Refer to Section 10.4.3.1 for the information on study continuation for participants who become pregnant during the study.

8.2.2. Clinical safety laboratory tests

Refer to Section 10.2.2 for the list of clinical laboratory safety assessments required by the protocol. These assessments must be conducted according to the clinical laboratory manual and the schedule of activities (Section 1.3). The analyses of these samples will be performed locally.

8.2.3. Study holding rules and safety monitoring

This study will be overseen by an iSRC operating under a charter and by a SRT (in a blinded manner). The iSRC is a group of GSK experts (clinicians, safety representatives and statisticians), independent from the HSV-targeted immunotherapy project team, with

a proper medical and scientific expertise to guarantee the safety and wellbeing of the participants.

The iSRC evaluation will take place approximately once a month until all participants complete Day 57 visit to review all accumulated safety data. In addition to the planned iSRC evaluations, ad hoc iSRC evaluations can be triggered if any potential safety issue is observed.

During an iSRC evaluation, the iSRC will determine whether any of the predefined holding rules (refer to [Table 10](#)) are met or whether there is any other safety signal, based on all available unblinded safety data.

8.2.3.1. Study Holding Rules

Holding rules to be applied during the Study Intervention Administration Phase are presented in [Table 10](#). Meeting any of these holding rules will trigger a hold of study intervention irrespective of number of participants enrolled and/or timing of the event.

- Holding rules 1a-1d will be monitored by the investigators on a continuous basis throughout the study. Meeting any of these holding rules will trigger a hold of study intervention administration, irrespective of number of participants enrolled and/or timing of the event.

If an investigator detects one of the holding rules mentioned above, the study intervention administration will be immediately put on hold. GSK will be immediately informed and the data will be entered in the eCRF. It is GSK's responsibility to put the study intervention administration on hold at all sites.

- Holding rules will be assessed by the iSRC during safety evaluations on unblinded data. Meeting any of these holding rules will trigger a hold of study intervention administration.

Of note, no formal holding rules will be applied for other safety data such as non-life-threatening SAEs (those that are not meeting the definition of holding rule 1b), missed visits due to study intervention related AEs, Grade 1 and Grade 2 solicited and unsolicited AEs in the 7-day follow-up period and unsolicited AEs collected from 7 to 28 days after study intervention administration (refer to [Section 10.3.10.1](#) for assessment of intensity). However, to the extent of their availability, these data will also be reviewed by the SRT and iSRC to allow an overall assessment of the benefit/risk ratio of study intervention administration.

Table 10 Study Holding Rules

[figure not shown]
Holding Rule	Event	Number of Participants
1a	Death or any life-threatening SAE , regardless of causality	≥ 1
1b	Any non-life-threatening SAE that can be reasonably attributed to the study intervention administration	≥ 1
1c	Any withdrawal from the study (by investigator's or participant's request) and/or study intervention administration, following a Grade 3 AE	≥ 1
1d	Any solicited administration site or solicited systemic AE leading to hospitalization , or necrosis at the injection site, with an event onset within the 7-day (Days 1-7) post-study intervention administration period	≥ 1
2a	Any Grade 3 solicited administration site AE (lasting 48 hours or more) in an investigational group, with an event onset within the 7-day (Days 1-7) post-study intervention administration period	≥ 25% (and ≥ 2 participants in each HSVTI group)
2b	Any Grade 3 solicited systemic AE (lasting 48 hours or more) in an investigational group, with an event onset within the 7-day (Days 1-7) post-study intervention administration period	≥ 25% (and ≥ 2 participants in each HSVTI group)
2c	Any Grade 3 unsolicited AE in an investigational group, that can be reasonably attributed to the study intervention administration, with an event onset within the 28-days (Days 1-28) post-study intervention administration period OR Any Grade 3 abnormality* in pre-specified hematological or biochemical laboratory parameters in an investigational group, between Day 1 and Day 29 post-study intervention administration period	≥ 25% (and ≥ 2 participants in each HSVTI group)

AE: adverse event; **SAE:** serious adverse event

*Grading of laboratory parameters will be based on the FDA Guidance for Industry "Toxicity Grading Scale for Healthy Adult and Adolescent Volunteers Enrolled in Preventive Vaccine Clinical Trials" (see [Table 18](#)).

[Figure 2](#) illustrates the probability to reach the study holding rules following study intervention administration:

- For holding rules 1, using a cut-off of 1/20, there is more than 80% chance that the holding rule is met for a study intervention with a true incidence rate above 8% and there is more than 36% chance that the holding rule is not met for a study intervention with a true incidence rate below 5%.
- For holding rules 2, using a cut-off of 5/20, there is more than 80% chance that the holding rule is met for a study intervention with a true incidence rate above 32% and there is more than 63% chance that the holding rule is not met for a study intervention with a true incidence rate below 20%.

Figure 2 Risk Assessment Curves for Study Holding Rules

If a holding rule is met, the investigator must suspend administration of the study intervention and inform GSK immediately (e.g. holding rules 1a-d). Refer to [Table 13](#) for contact information. GSK will inform the investigator if holding rules 2a-c are met.

The following communication sequence must be followed:

- The concerned study staff must put study interventions administration on hold.
- The concerned study staff must immediately inform their local GSK contact defined in [Section 8.3.3.1](#).
- LML will inform the CSL, who will then inform the iSRC chair and the SRT lead.
- All informed study staff will confirm to their local contact that action has been taken to provide appropriate documentation to GSK.
- GSK will further evaluate the case by the iSRC and GSK's GSB and will take the decision to restart the study intervention administration, modify or stop the study. All study staff will be informed about that final decision by their local GSK contact.

In case the study is put on hold while a participant is in the screening process, and the timing to conduct the first study intervention administration at Visit 1 (Day 1) would exceed the interval defined in [Table 2](#), all screening procedures as detailed in the SoA ([Table 1](#)) must be performed again. Data from this re-screening, if performed, must be encoded in the eCRF.

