8.3.2.1. Clinically significant abnormal laboratory findings

The investigator must review the laboratory report, document that the review occurred, and record any clinically relevant changes occurring during the study in the AE section of the eCRF. Clinically significant abnormal laboratory findings are those which are not associated with an underlying disease, unless judged by the investigator to be more severe than expected for the participant's condition.

- All clinically significant abnormal laboratory test values reported during the study or within 28 days after the last dose of study intervention should be repeated until the values return to normal/baseline, or until they are no longer considered significantly abnormal by the investigator. Refer to Section [10.3.7](#) for more information on clinically abnormal laboratory assessments that qualify as an AE or SAE.
- If such values do not return to normal/baseline after an interval judged reasonable by the investigator, the etiology of the abnormal value should be identified, and the sponsor notified.

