10.2.2. Protocol required safety laboratory assessments

The tests detailed in [Table 17](#) will be performed by a laboratory designated by the sponsor.

Table 17 Hematology and Biochemistry Read-Outs

Sampling Timepoint	Sub-cohort Name	Number of Participants	Component
Type of Contact and Timepoint			
Screening	All screened participants	≥ 50	Hemoglobin
Visit 1 (Day 1)			WBC differential
Visit 2 (Day 8)			Platelets
Visit 3 (Day 29)			ALT
Visit 4 (Day 36)			AST
Visit 5 (Day 57)	All participants	~50	Creatinine
			Blood urea nitrogen

ALT: alanine aminotransferase; **AST:** aspartate aminotransferase; **WBC:** white blood cells

Table 18 Toxicity Grading Scales for Hematology and Biochemistry Parameters Applicable for this Study

Component	Mild (Grade 1)	Moderate (Grade 2)	Severe (Grade 3)	Potentially Life-Threatening (Grade 4)
Hematology (Whole Blood)				
Hemoglobin (g/dL) - female	11.0 - 12.0	9.5 - 10.9	8.0 - 9.4	< 8.0
Hemoglobin (g/dL) - male	12.5 - 13.5	10.5 - 12.4	8.5 - 10.4	< 8.5
Hemoglobin (g/dL) - female change from baseline value	Any decrease - 1.5	1.6 - 2.0	2.1 - 5.0	> 5.0
Hemoglobin (g/dL) - male change from baseline value	Any decrease - 1.5	1.6 - 2.0	2.1 - 5.0	> 5.0
WBC increase (cell/mm ³)	10 800 - 15 000	15 001 - 20 000	20 001 - 25 000	> 25 000
WBC decrease (cell/mm ³)	2 500 - 3 500	1 500 - 2 499	1 000 - 1 499	< 1 000
Platelets decrease (cell/mm ³)	125 000 - 140 000	100 000 - 124 000	25 000 - 99 000	< 25 000
Biochemistry (Serum)				
ALT (increase by factor)	1.1 - 2.5 x ULN	2.6 - 5.0 x ULN	5.1 - 10 x ULN	> 10.0 x ULN
AST (increase by factor)	1.1 - 2.5 x ULN	2.6 - 5.0 x ULN	5.1 - 10 x ULN	> 10.0 x ULN
Creatinine (mg/dL)	1.5 - 1.7	1.8 - 2.0	2.1 - 2.5	> 2.5 or requires dialysis
Blood urea nitrogen (mg/gL)	23 - 26	27 - 31	> 31	Requires dialysis

ALT: alanine aminotransferase; **AST:** aspartate aminotransferase; **ULN:** upper limit of the normal range; **WBC:** white blood cells

The laboratory values provided in the table are taken from the FDA Guidance for Industry "Toxicity Grading Scale for Healthy Adults and Adolescent Volunteers Enrolled in Preventive Vaccine Clinical Trials" dated September 2007.

These laboratory values serve as guidelines and are dependent upon institutional normal parameters. Institutional normal reference ranges should be provided to demonstrate that they are appropriate.

10.3. Appendix 3: Adverse Events: definitions and procedures for recording, evaluating, follow-up, and reporting

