10.3.2. Definition of an SAE

An SAE is any untoward medical occurrence that:	
a. Results in death	
b. Is life-threatening	
Note: The term 'life-threatening' in the definition of 'serious' refers to an event in which the participant was at risk of death at the time of the event. It does not refer to an event, which hypothetically might have caused death, had it been more severe.

c. Requires hospitalization or prolongation of existing hospitalization	
Note: In general, hospitalization signifies that the participant has been admitted (usually involving at least an overnight stay) at the hospital or emergency ward for observation and/or treatment that would not have been appropriate in the physician's office or outpatient setting. Complications that occur during hospitalization are AEs. If a complication prolongs hospitalization or fulfills any other serious criteria, the event is serious. When in doubt as to whether "hospitalization" occurred or was necessary, the AE should be considered serious.

d. Results in disability/incapacity	
Note: The term disability means a substantial disruption of a person's ability to conduct normal life functions. This definition is not intended to include experiences of relatively minor medical significance such as uncomplicated headache, nausea, vomiting, diarrhea, influenza like illness, and accidental trauma (e.g. sprained ankle) which may interfere or prevent everyday life functions but do not constitute a substantial disruption.

e. Is a congenital anomaly/birth defect in the offspring of a study participant.	
f. Abnormal pregnancy outcomes (e.g. spontaneous abortion, fetal death, stillbirth, congenital anomalies, ectopic pregnancy).	
g. Other situations	

Medical or scientific judgment must be exercised in deciding whether reporting is appropriate in other situations. Important medical events that may not be immediately life-threatening or result in death or hospitalization but may jeopardize the participant or require medical or surgical intervention to prevent one of the other outcomes listed in the above definition should be considered serious. Examples of such events are invasive or malignant cancers; intensive treatment in an emergency room or at home for allergic bronchospasm; blood dyscrasias; and convulsions that do not result in hospitalization.

10.3.3. **Solicited events**

a. **Solicited administration site events**

The following administration site events will be solicited:

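### The laboratory limb of holding rule 2c counts Grade 3 values only, so a participant whose only severe value is Grade 4 is literally not counted

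*Protocol*

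**What the plan says.** Protocol 8.2.3.1, Table 10, sets the holding rules for the dosing phase. Meeting any of them triggers a hold. Rules 2a to 2c are applied by the iSRC on unblinded data, with a threshold of at least 25% of participants and at least 2 participants. Rule 2c has two limbs. The first counts related Grade 3 unsolicited adverse events (AEs). The second counts "Any Grade 3 abnormality* in pre-specified hematological or biochemical laboratory parameters in an investigational group", from Day 1 to Day 29 after a dose. The footnote refers grading to Table 18.

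Table 18 (Protocol 10.2.2) has a Grade 3 column and a further column whose heading begins "Potentially Life-Threatening (Grade 4". For hemoglobin, white cells, platelets, ALT, AST and creatinine, Grade 3 is a closed band and Grade 4 lies beyond it. ALT, for example, is Grade 3 from 5.1 to 10 times the upper limit of normal (ULN) and Grade 4 above 10. Blood urea nitrogen is the exception: Grade 3 is open-ended (above 31) and Grade 4 is defined by the need for dialysis.

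The protocol gives the operating characteristics in these terms: "For holding rules 2, using a cut-off of 5/20", the chance of a hold exceeds 80% at a true incidence above 32%, and the chance of no hold exceeds 63% at a true incidence below 20%.

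**The concern.** A holding rule should not become harder to meet as the findings get worse. Taken literally, this limb can. An ALT of 9 times ULN counts toward the threshold and an ALT of 12 times ULN does not. If five of 20 participants have Grade 3 values, the rule is met. If one of those five had a Grade 4 value instead, and nothing in the Grade 3 range, it is not.

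The wording matters only in this limb. The intensity scales for solicited and unsolicited events (Protocol Tables 22 and 23) stop at Grade 3, so *Grade 3* covers the top category in rules 2a, 2b and the AE limb of 2c. The laboratory scale alone continues to Grade 4.

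This limb is also the one part of rule 2c that needs no view on seriousness, causality or clinical significance. At stake is whether a mandatory, objective trigger in healthy volunteers counts the most severe values.

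**Working it through.** **Step 1. Reproduce the plan's figures for rules 2.** Inputs from Protocol 8.2.3.1: n = 20 per investigational group, hold at 5 or more. With X binomial(20, p),

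P(X ≥ 5) = 1 − Σ(k = 0 to 4) C(20,k) p^k (1 − p)^(20−k).

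- p = 0.32: the terms for k = 0 to 4 are 0.0004, 0.0042, 0.0188, 0.0531 and 0.1062, which sum to 0.183. P(hold) = 1 − 0.183 = 0.817. The protocol says more than 80%.
- p = 0.20: the terms are 0.0115, 0.0576, 0.1369, 0.2054 and 0.2182, which sum to 0.630. P(no hold) = 0.630. The protocol says 63%.

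Both figures reproduce. They are calculated for whatever event the rule counts and do not show whether Grade 4 is included.

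**Step 2. Apply the count both ways.** The threshold is 0.25 × 20 = 5 participants. Take four participants with a Grade 3 value and a fifth whose only value above Grade 2 is Grade 4, with no other rule triggered.

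| Reading | Counted | Share | Rule 2c |
|---|---|---|---|
| As written (Grade 3) | 4 of 20 | 20% | not met |
| Grade 3 or higher | 5 of 20 | 25% | met |

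**Step 3. Who is actually missed.** A Grade 4 value does not by itself remove a participant from the count, because any Grade 3 value on any row within the window is enough. Hemoglobin is graded both on its absolute level and on change from baseline:

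- A man falling from 15.0 to 9.5 g/dL has a change of 5.5 (Grade 4, above 5.0) and a level of 9.5 (Grade 3, 8.5 to 10.4). He is counted.
- A woman falling from 12.0 to 7.5 g/dL has a level below 8.0 (Grade 4) and a change of 4.5 (Grade 3, 2.1 to 5.0). She is counted.
- A man falling from 15.0 to 8.0 g/dL has a change of 7.0 and a level below 8.5, Grade 4 on both rows. With no Grade 3 value elsewhere, he is not counted.

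A repeat test in the Grade 3 range also brings a participant in. Protocol 8.3.2.1 says that clinically significant abnormal values "should be repeated until the values return to normal/baseline", but values not judged clinically significant need no repeat. The scheduled samples after Dose 1 are at Days 8 and 29, 21 days apart, so a value can go from Grade 4 to below Grade 3 between them unrecorded.

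**Step 4. Which other provisions catch the remainder.**

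| Provision | What it needs beyond the Grade 4 value |
|---|---|
| Rule 1a | Death or a life-threatening SAE; 10.3.2 requires actual risk of death at the time |
| Rule 1b | A serious event attributed to the intervention; 10.3.2 gives as examples of serious events "blood dyscrasias; and convulsions that do not result in hospitalization" |
| Rule 1c | Withdrawal from the study "and/or study intervention administration, following a Grade 3 AE"; under 10.3.7 a laboratory value becomes an AE only if judged clinically significant |
| Rule 2c, AE limb | A Grade 3 AE judged related |
| 8.2.3, iSRC review | A finding by the committee on "whether there is any other safety signal, based on all available unblinded safety data" |
| 8.2.3.2 | A safety concern recognised at a safety evaluation |
| 7.1.1 | Bars that participant's next dose, unless the value is judged temporary or not clinically significant |

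Each row requires a judgement that the laboratory limb of 2c does not. The participants still missed are mainly those with a Grade 4 value judged non-serious and either temporary, not clinically significant, or not recorded as a Grade 3 AE that stops dosing or is judged related.

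**The case against.** The strongest reply is that no safety committee would read *Grade 3* as leaving out Grade 4, and that the iSRC works under a separate charter which may say so. That is plausible. The charter is not among the documents, so the point concerns the protocol's wording and not what the committee will do.

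The second reply is that the remaining group is narrow. The participant must have no Grade 3 value on any row or repeat test, must escape rules 1a to 1c and the AE limb of 2c, and must be the deciding case at 25%. Even then the iSRC would have four Grade 3 participants and one Grade 4 participant in front of it, and 8.2.3.2 requires a hold for any safety concern. This stands, and it is why the practical effect is small. It does not make the wording right, because these routes rest on judgement and a predefined rule is meant to work without it.

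A reader might infer that misses are likely because every Table 18 parameter except blood urea nitrogen has a numeric Grade 4 limit. The documents do not support that. The number of parameters with such a limit says nothing about how often a participant has only Grade 4 values, and step 3 shows that one sample can be Grade 4 on one row and Grade 3 on another.

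**Conclusion.** The laboratory limb of rule 2c is wrong as written, and the matter is minor. At the protocol's own cut-off the wording can turn 5/20 = 25% (met) into 4/20 = 20% (not met). That result assumes a full group of 20, a fifth participant with no Grade 3 value in the window, and no other rule triggered by that participant.

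Two stronger readings should be resisted.

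- A reader might infer a measurable loss in the probability of a hold. That would need the share of affected participants who have only Grade 4 values and the chance that such a case triggers rule 1. The documents give neither. Rules 1a to 1c act on a single participant, so such cases can also bring a hold sooner than rule 2c would. The stated 80% and 63% are not disputed.
- A reader might infer that the note in 8.2.3.1, which places unsolicited AEs from 7 to 28 days outside formal rules, conflicts with the Days 1 to 28 window of rule 2c. On the better reading Table 10 governs: the note concerns data other than those the rules cover, and the section opens by making holds independent of the timing of the event. No change is needed there.

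**What to change.** In the laboratory limb of rule 2c in Table 10, write *Any Grade 3 or higher abnormality*. Confirm that the iSRC charter uses the same wording, since the iSRC applies this rule.

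The cost is one short wording change and a document check. No data, visits or participants are added, and the 5/20 cut-off and its stated operating characteristics stay as they are. Under Protocol 10.1.1 a protocol amendment needs ethics committee approval before it takes effect, so the change can go in with the next amendment, with the charter stating the reading in the meantime.
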